# Participant reimbursement

In Brazil, Resolution No. 466 of December 12, 2012 outlines the guidelines and regulatory standards for research involving humans in Brazil. This resolution outlines the requirement to provide reimbursement to participants and their companions, when necessary, such as transportation. In line with this requirement, participants in Brazil will receive reimbursement for relevant transportation costs for participation in the BRACE trial.

## Safety Reporting

In Brazil, the RPI/s and SPI/s must comply with the safety reporting requirements of CEP/CONEP (defined in Circular Letter number 13). The HREC/s must be notified of all SAEs through the Brazil Platform (Notification), after the end of the event. The following timelines will be met for this study:

- 1. 30 days in case of fatal SAE occurring in a participant of the site in the jurisdiction of the HREC
- 2. 7 days in case of an SAE with a causal relationship with the investigational product, in a participant of the site in the jurisdiction of the HREC (Casual relationship means that the SAE is judged by either the reporting investigator or the sponsor as having a reasonable possibility of a causal relationship to a study vaccine).
- 3. 6 months for other SAE.

The RPI (or delegate) will notify SUSAR in Brazil to all investigators in their region, as appropriate. The RPI (or delegate) will report significant safety issues (including USM) to SPI in their region, the regulatory authority and applicable HREC/s in accordance with the requirements. The RPI (or delegate) will provide periodic reports of SAE (from Brazil trial sites) to the applicable regulatory authorities and/or HREC/s, as appropriate.

## 17.5 Appendix 5 The Netherlands Specific Requirements

The following changes will apply for the performance of the protocol in the Netherlands:

#### Statement of Compliance

This clinical trial will be conducted in compliance with all stipulations of this protocol, the conditions of the ethics committee approval, the NHMRC National Statement on ethical Conduct in Human Research (2007 and all updates), the Integrated Addendum to ICH E6 (R1): Guideline for Good Clinical Practice E6 (R2), dated 9 November 2016 annotated with TGA comments and the NHMRC guidance Safety monitoring and reporting in clinical trials involving therapeutic goods (EH59, 2016), and General Data Protection Regulation (GDPR), as well as local laws and regulations, such as the Wet medisch-wetenschappelijk onderzoek met mensen (WMO).

# 2. Recruitment and consent

In Europe, due to ethics regulations, an electronic PICF will not be used and no information on eligibility nor any contact information will be collected prior to the informed consent process being finalized. When participants are interested in the study, they can verify their eligibility with the criteria listed on the website. Then, they will be shown a list of participating centers and advised to contact one of the centers directly to make an appointment for the first study visit. At this visit, the informed consent procedure will be completed in a face-to-face setting where the PICF will be read and signed by both participant and investigator. Exact date of birth will not be collected in the eCRF for the study due to GDPR constraints; instead, year of birth (or 01-01-yyyy) will be used in the eCRF.

- 3. Data capture methods and data use, storage, access and disclosure during the trial
  Archiving will be in compliance with NFU requirements: study data, source documents and the Study File will be kept for 25 years.
  EU protocol addendum page V2.0 20200629
- 4. COVID-19 testing will be performed via the national testing policy and therefore, the General Practitioner will be notified of the results by the organisation that performs the testing: GGD or the hospital that performs the test.

#### 5. Sharing of contact information

In order to send out the 3, 6, 9, and 12 month questionnaires, the participant's email address will be collected in the REDCap database. No other identifying information will be stored in the database for EU participants.

6. BCG vaccination is not expected to cause an exacerbation of the immune response with adverse consequences, because of 3 main arguments: • By activating anti-viral mechanisms, BCG decreases virus load and systemic inflammation (Arts et al, Cell Host Microbe 2018). Influenza pathophysiology is the same so if BCG had adverse effects, this would have been known for a long time. • Information is available on individuals vaccinated with BCG last year and no COVID19 complications were observed in this group.

## 17.6 Appendix 6 Spain Specific Requirements

The following changes will apply for the performance of the protocol in Spain:

#### 1. Statement of Compliance

This clinical trial will be conducted in compliance with all stipulations of this protocol, the conditions of the ethics committee approval, the Integrated Addendum to ICH E6 (R1): Guideline for Good Clinical Practice E6 (R2), dated 9 November 2016 and General Data Protection Regulation (GDPR), as well as local laws and regulations

#### 2. Inclusion criteria

According to recommendations of the competent authority AEMPS (Agencia Española del Medicamento y Productos Sanitarios) If the patient is female, and of childbearing potential, she must have a negative pregnancy test (provided by Sponsor) at the time of inclusion and practice a reliable method of birth control for 30 days after receiving the BCG vaccination. - Woman of Childbearing Potential is defined as a premenopausal female who is capable of becoming pregnant.

#### 3. Recruitment and consent

In Europe, due to ethics regulations, an electronic PICF will not be used and no information on eligibility nor any contact information will be collected prior to the informed consent process being finalized. When participants are interested in the study, they can verify their eligibility with the criteria listed on the website. Then, they will be shown a list of participating centers and advised to contact one of the centers directly to make an appointment for the first study visit. At this visit, the informed consent procedure will be completed in a face-to-face setting where the PICF will be read and signed by both participant and investigator.

Exact date of birth will not be collected in the eCRF for the study due to GDPR constraints; instead, year of birth (or 01-01-yyyy) will be used in the eCRF.

4. Data capture methods and data use, storage, access and disclosure during the trial
Archiving will be in compliance with NFU requirements: study data, source documents and the Study File will be kept for 25 years.

## 5. Sharing of contact information

In order to send out the 3, 6, 9, and 12 month questionnaires, the participant's email address will be collected in the REDCap database. No other identifying information will be stored in the database for EU participants.

## 17.7 Appendix 7 Optional Biological sample collection during episodes of illness

Assessment of immune responses during episodes of illness will provide crucial insights into the mechanisms by which BCG may protect against COVID-19. BCG is proposed to protect against unrelated infections by boosting the innate immune response which can directly protect against infections and also shape the adaptive immune response. Biological samples collected after infection provide meaningful insight into the long-lasting effects of the infection and immune memory. However, they do not provide information about the early immune response to infection that can promote early clearance, may impact disease severity and may define the long-lasting memory response. It is this part of the immune response where BCG vaccination may play a crucial role in protection against COVID-19 as well as non-COVID-19 respiratory infections.

#### Objectives of exploratory sub-study

The additional collection of biological samples from BRACE participants during episodes of febrile or respiratory illness will contribute to the planned subgroup exploratory analyses of BRACE:

- 11. To determine the impact of BCG vaccination on the immune system that are associated with protection of adult healthcare workers from non-tuberculous infectious diseases including COVID-19.
- 13. To identify factors (e.g. age, sex, chronic conditions such as diabetes and cardiovascular disease, smoking, asthma, prior BCG vaccination, genetics, influenza vaccination, immunological/molecular factors) that influence adult immune responses and COVID-19 responses.

It will also contribute to the following additional exploratory objectives: In a sub-set of BRACE trial participants who consent for an optional biological sample to be collected during episodes of fever or respiratory illness:

- To characterise the immune response to SARS-CoV-2 infection
- To compare immune responses during an episode of respiratory illness (COVID-19 or non-COVID-19 illness) in BCG-vaccinated and non-BCG vaccinated participants

#### Outcomes:

Immune system characterisation and molecular markers of disease in episodes of COVID-19 or non-COVID-19 respiratory or febrile illness from BCG-vaccinated and non-vaccinated participants.

**Population:** A sub-group of the BRACE trial participants who consent to an optional biological sample to be collected during episodes of fever or respiratory illness.

## Study Duration:

As per the BRACE trial protocol – 2 years.

#### Participant Duration:

12 months from randomisation.

## **Sub-study Locations:**

Optional inclusion for Australian sites.

#### Potential risks and benefits:

# Known potential risks:

This sub-study involves minimal risk to participants. Having a blood test can sometimes cause some pain from the needle or be uncomfortable. Occasionally a small amount of bruising can occur on the skin where the blood was taken. Trained members of the study team will collect the blood samples from participants. Having a respiratory swab can sometimes be uncomfortable. Trained members of the study team will collect the respiratory swabs from participants. Self-testing swab kits may be provided as required, with clear instructions to participants on safe self-swabbing technique.

## Known potential benefits:

This sub-study is exploratory in nature and is not expected to provide any direct additional benefit to the participants. The findings of the study, however, may be of significant value for understanding the immune response to COVID-19, the off-target effects of BCG vaccination on responses to COVID-19 and other respiratory infections and determinants of disease severity.

#### Sub-study design:

#### Consent:

An additional option has been added to the BRACE online consent form to allow participants to optionally consent additional biological sample collection during an episode of illness. The BRACE participant information and consent form (PICF) has been also modified to explain to participants the process for collecting these additional blood samples and why they are being collected. If a participant declines to consent for additional biological sample collection during an episode of illness this will not affect their participation in the BRACE trial (assuming all other inclusion and exclusion criteria are met).

## Sample collection process:

Participants consenting for additional biological sample collection during an episode of illness may be contracted by the study team during any episode of respiratory or febrile illness that occurs during their involvement in the BRACE trial (i.e. up to 12 months from randomisation). Sample collection would occur during and up to one month after resolution of an episode of illness with fever or respiratory symptoms. The collection of samples will be done at a study

site (e.g. if they are inpatients or obtaining SARS-CoV-2 testing at a study site) or at the participant's home, depending on the location of the participant.

Samples to be collected are:

-a blood sample

and/or

- saliva/respiratory swab/s

All samples will be collected, processed and stored in accordance with the BRACE trial protocol section 7.3. We will aim to take these samples at the same time as any other clinical or research samples where possible to minimise the number of sample collections for each participant, minimise contact of research staff with infectious patients and to reduce the need for research staff to use vital personal protective equipment (PPE).

#### What we will do with the sample:

Samples will be processed for analysis of the immune system as detailed in BRACE trial protocol section 3.2. Where indicated, saliva/respiratory swab/s collected will be linked with the relevant public health testing and reporting systems as BRACE trial protocol section 7.3. In addition, samples will be included in the BRACE biobank if participants have also consented for their samples being placed in the BRACE biobank.

#### Sub study locations:

Australia Brazil

#### Overview:

COVID-19-specific vaccines are becoming increasingly available and healthcare workers, being at high risk of SARS-CoV-2 exposure, are prioritised for receipt of these vaccines. BCG vaccination alters immune responses to subsequence vaccinations and therefore it is plausible that it may boost the immune response to COVID-19-specific vaccines. As healthcare workers, participants in the BRACE trial will be prioritised for receipt of COVID-19-specific vaccines in most regions and as a result will likely receive these vaccines during their involvement of the BRACE trial.

The type of COVID-19-specific vaccine given to BRACE trial participants will vary between sites and it is likely that more than one type of vaccine will be used in a given region. The number of doses given (one or two) and the recommended interval between the two doses are likely to vary as well but are likely to be consistent within a given region.

The BRACE trial exploratory outcomes already include assessment of the effects of vaccines on the immune system (including the effects of BCG-vaccination on immune response to COVID-19-specific vaccines).

To ensure we obtain samples at the optimal times before and after COVID-19-specific vaccination, in a subset of participants, we propose collecting blood samples at up to three additional time-points:

- (Visit 1, site specific) prior to receipt of the first dose of a COVID-19-specific vaccine.
- (Visit 2, site specific) after the first dose of a COVID-19-specific vaccine.
- (Visit 3) 28 days after the second dose of a COVID-19-specific vaccine.

These additional blood samples enable us to:

- screen for prior SARS-CoV-2 exposure (accounted for at analysis), and provide a baseline measure of the immune system prior to receipt of COVID-19-specific vaccines.
- measure the immune response (e.g. antibodies) to the first and second dose of COVID-19-specific vaccines, and other changes in the immune system induced by the COVID-19-specific vaccine.
- compare the vaccine responses to COVID-19-specific vaccines between the BCG and the control group to each COVID-19 specific vaccine.
- compare our findings to other studies on COVID-19-specific vaccines.

Determining if BCG vaccination can improve the immune response to COVID-19-specific vaccines have important implications for the potential of BCG vaccination to increase efficacy of COVID-19-specific vaccines and may also impact our interpretation of the outcomes of the BRACE trial. This is particularly important for the COVID-19-specific vaccines that have a lower efficacy.

## Objectives of exploratory sub-study

The additional collection of blood samples from BRACE trial participants immediately prior to, and after each COVID-19-specific vaccination will contribute to the existing planned subgroup exploratory analyses of BRACE:

- 1. To determine the impact of BCG vaccination on the immune system that are associated with protection of adult healthcare workers from non-tuberculous infectious diseases including COVID-19.
- 2. To determine and compare changes in the immune system induced by vaccination of adult healthcare workers.
- 3. To identify factors (e.g. age, sex, chronic conditions such as diabetes and cardiovascular disease, smoking, asthma, prior BCG vaccination, genetics, other vaccinations including COVID-19-specific vaccines, latent TB, immunological/molecular factors) that influence adult immune responses, infection and COVID-19 risk.

**Population:** A sub-group of the BRACE trial participants who receive COVID-19-specific vaccines in regions taking part in the sub-study.

**Outcomes:** Immune system characterisation and molecular markers of immunity (including seroconversion to SARS-CoV-2) in response to COVID-19-specific vaccines in BCG-vaccinated and non-BCG-vaccinated participants.

**Study Duration:** As per the BRACE trial protocol – 2 years.

Participant Duration: Up to 4 months from sub-study inclusion

Sub-study Principal Investigator: [name]

#### Potential risks and benefits

#### Known potential risks

This sub-study involves minimal risk to participants. Having a blood test can sometimes cause some pain from the needle or be uncomfortable. Occasionally a small amount of bruising can occur on the skin where the blood was taken. Trained members of the study team will collect the blood samples from participants.

The amount of blood collected is too small to have any impact on the participants' health. This sub-study will not impact the setting up of COVID-19-specific vaccination clinic at the participating sites. It is not expected to have any negative interactions between the BCG and the COVID-19-specific vaccine.

## Known potential benefits

This sub-study is exploratory in nature and is not expected to provide any direct additional benefit to the participants. The findings of the study, however, may be of significant value for understanding the immune response to COVID-19-specific vaccines and the off-target effects of BCG vaccination on responses to COVID-19-specific vaccines.

#### Sub-study design

## Eligibility:

#### Inclusion Criteria

- Participant in the BRACE trial who has previously consented to be contacted for future ethically approved projects.
- Participant recruited to the BRACE trial at a site taking part in this sub-study.

#### Exclusion Criteria

- A previous positive SARS-CoV-2 test at any time (not applicable in Brazil).
- Expected inability to provide a blood sample in the indicated time window after: the first dose (visit 2) and/or the second dose (visit 3) of a COVID-19-specific vaccine.
- [site specific]: Inability to provide a blood sample in the indicated time window prior the first dose (visit 1) of a COVID-19-specific vaccine.

## Recruitment

Potential BRACE participants will be informed of this sub-study and invited to participate as per their recruitment sites' existing communication approach. BRACE participants will evaluate their eligibility for the sub-study and will have access to the site-specific participant information and consent form (PICF) prior to enrolment in the sub-study.

#### Consent

An additional participant information and consent form (PICF) will be provided to participants to allow them to optionally consent to this sub-study. If a participant declines to consent for this sub-study it will not affect their participation in the BRACE trial.

#### Data collection

Participants interested in this sub-study will be contacted by the study team to arrange blood collection if:

• The BRACE trial study site from which they were recruited begins COVID-19-specific vaccinations of staff

Or

• if the participants inform the BRACE trial team that they will receive a COVID-19 specific vaccine.

At these additional sub-study visits, participants will be asked about:

- prior positive COVID-19 tests,
- any other vaccines received since randomisation in BRACE (type, dose, route, date)

- expected date of vaccination with COVID-19-specific vaccine and which vaccine
- episodes of febrile or respiratory illness since last visit (if not already collected as part of the BRACE trial)
- (after vaccination only) adverse reaction to the COVID-19-specific vaccine After the expected COVID-19-specific vaccine administration date, participants will be contacted as per their recruitment sites' existing communication approach, to confirm which vaccine they have received, where and when they received it, as well as when is the second dose planned.

## Sample collection process

Sample collection will occur:

 (Visit 1, site specific) On the day of (or in the 5 to 14 days preceding) the first dose of a COVID-19-specific vaccine.

[site specific] Note that for a participant who has already received their first dose of a COVID-19 specific vaccine, the participant's blood sample for the first timepoint will not need to be collected. However, blood samples for the remaining time points below will need to be collected.

It is planned to collect blood samples on the same day of vaccination, however we will accept bloods that are taken up to 5 days before the first dose of COVID-19 specific vaccine in all regions, or even up to 14 days before the first dose of COVID-19 specific vaccine in regions where the COVID-19 prevalence is low, are acceptable.

 (Visit 2, site specific) 1 to 28 days (±2) days after the first dose of a COVID-19-specific vaccine

Note that where the second dose of the COVID-19 specific vaccine is given within 28 days in a given region, this sample will be taken at an earlier time point. Efforts will be made to standardise the interval between the first dose of COVID-19-specific vaccine and the blood sample for each type of COVID-19-specific vaccine within each given region, e.g. within 14 ( $\pm 2$ ) days after the first dose of COVID-19-specific vaccine if the two doses of COVID-19-specific vaccine are given 2 weeks apart, or within 21 ( $\pm 2$ ) days after the first dose of COVID-19-specific vaccine if the two doses of COVID-19-specific vaccine are given 3 weeks apart.

In specific sites, an earlier time-point (<7 days) will enable the exploration of the initial gene expression responses to vaccination.

• (Visit 3) 28 (±2) days after the second dose of a COVID-19-specific vaccine

Note that efforts will be made to standardise the interval between the COVID-19-specific vaccine doses and the blood collection for both blood collections, for each type of COVID-19-specific vaccine and within a given region.

Blood samples will be collected, processed and stored in accordance with the BRACE trial protocol section 7.3 with the exception that up to 40 mL of blood will be taken at each time point. Also, if this blood collection is done at the same time as a BRACE trial 3-monthly blood collection, an additional 10 mL of blood may be required for a total of 50 mL. The collection of blood samples will be done at a study site or at the participant's home, depending on the region. We will aim to collect these samples at the same time as the existing BRACE Trial 3-monthly blood samples where possible, to minimise the number of sample collections for each participant.

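### In the optional COVID-19-vaccine sub-study, the Visit 2 tolerance lets the post-dose-1 blood sample be drawn up to 2 days after dose 2, and the Visit 1 bullet does not match its own note

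*Protocol*

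**What the plan says.** All the timing text is in the Protocol, section 17.8 (Appendix 8), Sample collection process.

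- **Visit 1, bullet:** "On the day of (or in the 5 to 14 days preceding) the first dose of a COVID-19-specific vaccine", with no regional condition.
- **Visit 1, note below the bullet:** "we will accept bloods that are taken up to 5 days before the first dose of COVID-19 specific vaccine in all regions", extended to "up to 14 days before the first dose of COVID-19 specific vaccine in regions where the COVID-19 prevalence is low". Low prevalence is not defined.
- **Visit 2, bullet:** "1 to 28 days (±2) days after the first dose of a COVID-19-specific vaccine".
- **Visit 2, note:** the draw is brought forward if dose 2 comes soon: "where the second dose of the COVID-19 specific vaccine is given within 28 days in a given region, this sample will be taken at an" (the sentence closes by naming a sooner point than the general window). The first example gives 14 (±2), introduced by the word within, for "days after the first dose of COVID-19-specific vaccine if the two doses of COVID-19-specific vaccine are given 2 weeks apart". The second is within 21 (±2) days for a 3-week interval.
- **Visit 3:** 28 (±2) days after the second dose.

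The Overview of the same appendix says that the extra samples are there to "measure the immune response (e.g. antibodies) to the first and second dose of COVID-19-specific vaccines", to screen for earlier SARS-CoV-2 exposure, and to compare BCG with control. The exclusion criteria refer to ability to give blood in the indicated windows, so the windows also bear on who enters the sub-study.

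**The concern.** A sample meant to show the response to dose 1 has to be taken before dose 2 is given. Appendix 8 moves the draw earlier when the second dose comes soon, but its examples place the draw at the dose interval itself and add a two-day tolerance. A sample taken one or two days after dose 2 would carry some early response to that dose into the dose-1 result. The assays include immune-cell activation and function as well as antibodies, so such a draw is not clearly harmless.

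Visit 1 is the baseline for each participant and the screen for earlier infection. If one site works from the bullet and another from the note, they accept different baseline samples and, where the Visit 1 exclusion applies, may enrol different people. An older baseline leaves more time for an unrecorded infection before dose 1.

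**Working it through.** The plan gives no figure to reproduce. The check is day arithmetic, with day 0 as the day of dose 1 and all inputs taken from the Sample collection process text.

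**Visit 2, upper limit.** Latest day = nominal day + 2. Overrun = latest day - day of dose 2.

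| Dose interval | Nominal day | Latest day | Overrun past dose 2 |
|---|---|---|---|
| 14 days (example) | 14 | 14 + 2 = 16 | 16 - 14 = 2 days |
| 21 days (example) | 21 | 21 + 2 = 23 | 23 - 21 = 2 days |
| 28 days (general window) | 28 | 28 + 2 = 30 | 30 - 28 = 2 days |

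The third row assumes that dose 2 is given on day 28 and that the general window stays in force. If an interval of exactly 28 days counts as being within 28 days, the draw is moved earlier, but the text does not say to when. The first two rows use the plan's own examples and need only that dose 2 is given on schedule.

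The overrun does not depend on how the examples are read. As a band around a target, 14 (±2) is days 12 to 16. As a latest permitted day, it ends at day 14 with a tolerance to day 16. Both end at day 16. Appendix 8 contains no sentence placing the draw before dose 2.

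**Visit 2, lower limit.** With the tolerance on both ends, 1 - 2 = day -1 and 28 + 2 = day 30. With the tolerance on the upper end only, the window is day 1 to day 30. The bullet does not say which is meant.

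**Visit 1, bullet against note.**

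- Bullet, read literally: day 0 and days -14 to -5.
- Note, all regions: days -5 to 0.
- Note, low-prevalence regions: days -14 to 0.

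Days allowed by the note but not by the bullet are -4, -3, -2 and -1, which is 4 days, in every region. Days allowed by the bullet but not by the note are -14 to -6, which is 9 days, in regions that are not low-prevalence. In those regions the two texts agree only on day 0 and day -5.

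**Visit 3.** 28 - 2 = 26 and 28 + 2 = 30 days after dose 2. There is no conflict.

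The number of samples actually drawn on disputed days cannot be derived, because the Protocol gives no distribution of draw dates.

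**The case against.** The best defence is that the appendix can be read sensibly as it stands. Several stronger claims that a reader might infer do fail:

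- **Baseline samples 14 days old in high-prevalence Brazil.** This follows only if the bullet is read without its note, which holds regions that are not low-prevalence to 5 days. The bullet may be shorthand for 5 or 14 days according to region. The Protocol gives no prevalence figure for Brazil; Appendix 4 mentions high transmission in Rio de Janeiro only, in connection with baseline swabs.
- **A Visit 2 sample before dose 1.** Day -1 appears only when ±2 is applied to the lower limit, against the plain statement that the sample follows the first dose. This is loose drafting, not a permitted draw.
- **Two of five permitted days fall after dose 2.** The examples say within 14 or 21 days, which can be an upper limit. On that reading most permitted days come before dose 2 and no five-day band exists.
- **Stated reasons for the rules.** The text does not say why the Visit 2 draw moves earlier or why 14 days is limited to low-prevalence regions. Any reason is an inference.
- **A fault around every dose.** The Visit 3 window is consistent.

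The harm is also limited. Early gene-expression work has its own time-point, under 7 days, at specific sites. Participants are asked about earlier positive tests and illness, and prior exposure is to be accounted for in the analysis. Section 7.3 puts the expected antibody peak about one month after symptom onset, so even a same-day baseline can miss a recent infection. Handling of late draws could be set out in an analysis plan that is not shown.

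What this does not answer is that the tolerance passes dose 2 on either reading of the examples, that nothing requires the draw to come first, and that the Visit 1 bullet and note do not say the same thing.

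**Conclusion.** The point holds as a minor one. The Visit 2 rule allows a sample labelled as following dose 1 to be taken up to 2 days after dose 2, in the plan's own 2-week and 3-week examples and also at 28 days if the general window applies. That is a real route for mixing the two dose responses that the appendix wants to measure. It rests on dose 2 being given at the nominal interval and on the tolerance being used in full; how often that happens is unknown.

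The Visit 1 mismatch, the undefined term low prevalence and the unplaced ±2 are drafting faults that sites could resolve differently. The documents do not show that any sample was taken outside the intended window. The effect is confined to an optional exploratory sub-study with no formal sample size calculation, and the trial's primary and secondary outcomes are not touched.

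**What to change.** In Appendix 8, Sample collection process:

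1. **Visit 2:** state that the sample is drawn after dose 1 and in every case before dose 2 is given, and that ±2 does not apply to the lower limit. This governs the blood draw only, not the timing of any vaccine dose.
2. **Visit 1:** align the bullet with its note: the day of dose 1 or up to 5 days before, and up to 14 days before only in low-prevalence regions. State what counts as low prevalence.
3. **Samples already drawn:** use recorded vaccination dates to exclude Visit 2 samples taken after dose 2 from the dose-1 comparison. Flag Visit 1 samples older than 5 days from regions that are not low-prevalence. The check needs the actual date of dose 2, not the planned one. For a draw on the same day as dose 2 it also needs the order of the two; section 7.3 has the collection time on the sample label.

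The cost is a few lines of wording, one date check, and the loss of a few samples from the dose-1 comparison.
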